8.1. Overview

We will conduct a Stage 1 pilot feasibility study at McLean Hospital to develop a combination of medication protocol to treat cannabis dependence in subjects with schizophrenia, schizoaffective, or any Axis I disorder. In a randomized, double-blind, placebo-controlled trial, 18 cannabis-dependent male an female subjects ages 18-45 with an Axis 1 psychiatric disorder will receive medical management (MM) over a 10-week period, with half receiving treatment with the combination of dronabinol and clonidine and half receiving placebo. Subjects will receive either the combination of dronabinol 5 mg by mouth three times daily and clonidine 0.1 mg my mouth twice daily or placebo in addition to MM over a 10-week treatment period. A follow-up visit after treatment at week 14 will evaluate the durability of treatment effects on drug use and psychosocial outcomes. Primary outcomes will include self-report of cannabis smoking and results of quantitative urine drug screens for cannabis. We also will assess cannabis withdrawal symptoms, including mood and craving. Mixed models ANOVA will be used to analyze the data.

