8.2. Participants

Subjects are cannabis-dependent male and female volunteers with mental illness ages 18-45 years old and will be recruited via newspaper advertisements, word of mouth, web-based advertisements, and the Psychotic Division Clinical Research Core (Protocol # 2009-P-002016)..

A total of 18 cannabis-dependent volunteers with (9 men, 9 women) an Axis 1 psychiatric Disorder will serve as subjects. Factoring in a potential 20% dropout of those who actually begin the protocol, we estimate that 7-8 people will probably be exposed to dronabinol in this pilot study. In order to meet the target sample of 18 completers (8 subjects per group), we expect to recruit about 50 subjects and have 35 sign the informed consent form. Of those who sign the informed consent form, 14-18 will probably end up being randomized.

Women must use a medically-approved method of contraception to participate in the study (e.g. birth control pills, IUD, condoms). During the physical, the physician will ensure that the potential volunteer is using adequate methods to prevent pregnancy.

Briefly describe study procedures. Include any local site restrictions, for example, "Subjects enrolled at McLean will not participate in the pharmacokinetic portion of the study." Describe study endpoints.

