8.5.2.c. Other Drug and Alcohol Use Assessment. Severity of cannabis and other substance use and its associated problems will be assessed at baseline and weeks 5,10, and 14 with the Addiction Severity Index (ASI, 5th edition) (McLellan et al. 1992), a widely-used and independently-validated interview that measures the severity of problems in 7 areas of functioning that are frequently affected in patients with SUDs: drug use, alcohol use, employment, legal status, medical condition, social functioning, and psychological status. In addition to our primary focus on marijuana use (urine screens plus days of use), we will examine other substance use (using urine screens plus days of other substance use). We will use this method to determine the number of days of marijuana use and of any substance use (and conversely, days of abstinence). We will examine ASI composite scores as secondary measures of substance use outcome. We will also use the self-administered Drug and Alcohol Use Questionnaire. This measure, administered at baseline, addresses the context of lifetime and recent drug and alcohol use, as well as sociodemographic data. At each treatment visit, patients will complete a brief Weekly Drug and Alcohol Use Inventory, indicating their number of days using marijuana, other drugs, and alcohol during the previous week. The Marijuana Goals Questionnaire (Griffin et al. 1989) is a brief guestionnaire administered at baseline to assess treatment goals, specifically, whether a subject is seeking abstinence or reduction in marijuana use. A 12-item self-administered questionnaire, the Marijuana Craving Questionnaire, will be used to assess craving at

Partners Human Subjects Research Application Form

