All data collected will be de-identified with subject ID numbers and used for research purposes only. Written records will be kept in a locked file cabinet in a locked office. They will be destroyed after 5 years. Computerized data files will also be de-identified with subject ID numbers and kept in a password protected file on a password protected computer.

8.9. Statistical Analysis

The primary data analysis will be an intent-to-treat analysis, which includes all randomized subjects. Of note, every attempt will be made to continue assessing subjects even if they drop out of treatment. In addition, we will replicate all analyses with the completers only. The primary and secondary outcome variables are intended to

Partners Human Subjects Research Application Form Version Date: July 26, 2016

explore various aspects of response to therapy and to help define a clinically meaningful response. The primary outcome measures, Actiwatch-scores, daily diaries, TLFB self-report data, in addition to quantitative urinary THC metabolites, have been chosen for their ability to indicate daily use of cannabis by relying on self-report of use.

Specifically, for assessing the effect of dronabinol and clonidine on cannabis use patterns, we propose to use the generalized estimating equations (GEE) approach to longitudinal analysis, appropriately accounting for the positive correlation among repeated urine screen assessments within the same individual.

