Analyses of secondary substance use outcomes will focus on the number of days of cannabis use and of any substance use (and conversely, days of abstinence) during treatment and post-treatment follow-up. In addition, we will also examine the ASI Drug and Alcohol composite scores. Frequency of days of cannabis use (and any substance use and days of abstinence) will be analyzed via a log-linear (or Poisson) regression model, controlling for pre-treatment frequency of days of cannabis use. Although loglinear regression methods are considered appropriate for the analysis of count or frequency data, in many biomedical applications, count data have variability that far exceeds that predicted by the Poisson distribution; we expect that days of cannabis use (and any substance use and days of abstinence) will not be an exception. Linear mixed effects models will be used to examine the effect of treatment group on changes in the ASI Drug and Alcohol composite scores during treatment and post-treatment follow-up assessments (as determined by the group-by-time interaction in the linear mixed effects regression models). The linear mixed effects model will include random intercepts and slopes to appropriately account for correlation among repeated measures and heterogeneity of variance over time; the model will be fit using PROC MIXED in SAS.

In secondary analyses of mood outcomes, mood episodes will be assessed during treatment and post-treatment follow-up, using the QIDS-SR, , BAI, and BIS-11; ; changes in risk of mood episodes during treatment and post-treatment follow-up assessments will be analyzed via a logistic regression model (similar to the logistic model above) that will be fit using the GEE approach (as implemented in PROC GENMOD in SAS) to account for correlation among repeated binary outcomes on the same individual. To examine the effect of dronabinol and clonidine on changes in risk for mood episodes during treatment and post-treatment follow-up, the logistic regression model will include the effects of treatment condition and the baseline measure of the outcome.

For studies involving treatment or diagnosis, provide information about standard of care at McLean (e.g., BWH, MGH) and indicate how the study procedures differ from standard care. Provide information on available alternative treatments, procedures, or methods of diagnosis.

The standard of care for cannabis dependence is psychotherapy; our treatment centers upon a medication.

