During the 10-week treatment period, subjects will be seen for a MM visit and for urine screen visit. Medication compliance and side effects will be monitored at all visits. The initial visit in week 1 will include a monitored administration of medication described above. Subjects will have follow-up visits at 5, 10 and 14 weeks that will include a urine screen, blood sampling for laboratory testing, as well as evaluation for medication side effects.

Stopping Criteria. New psychotic symptoms thought to be related to dronabinol administration that are present at any pre-dose assessment or that remain present at the end of a 2-hour monitoring period will result in stopping of dronabinol. Clonidine stopping criteria include bradycardia less than or equal to 50 bpm, supine blood pressure of less than or equal to 100/65, a seated blood pressure of less than or equal to 90/60, or orthostatic change of >20 systolic or >10 diastolic on standing, at screening or any pre-dose assessment, or symptoms attributable to low BP (i.e. lightheadedness or dizziness on standing). Adverse events or side effects resulting from administration of either dronabinol or clonidine that persist beyond 7 days will warrant a call to the subjects PCP if they have one, and a decision will be made by the study physician about possible continued participation. If the subject is stopped, they will be followed for follow-up visits only.

Clinically significant lab abnormalities (liver function tests ≥3X normal, for example) will be rechecked immediately and, if determined to be clinically significant by the study

Partners Human Subjects Research Application Form

Version Date: July 26, 2016

physician, the subject will be removed from the protocol and followed for follow-up visits only. Worsening psychotic symptoms that predated study medication will warrant a call to the subject's psychiatrist and possible removal from the protocol if the patient is thought to be unstable by either the outpatient psychiatrist or the study physician. Similarly, suicidal ideation will warrant contact with the outpatient psychiatrist and possible removal from the protocol. Suicidal ideation with a plan will result in immediate removal from the protocol and the subject will be escorted by staff to the Psychiatric Emergency Room.

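### The day-count model in 8.9 states no exposure term or rule for unobserved days, so the ratio is biased if observed days differ between arms and loses power if they do not

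*Combined protocol and SAP*

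**What the plan says.** Section 8.9 Statistical Analysis defines the secondary substance use outcomes as the "number of days of cannabis use and of any substance use (and conversely, days of abstinence) during treatment and post-treatment follow-up". Their frequency "will be analyzed via a log-linear (or Poisson) regression model, controlling for pre-treatment frequency of days of cannabis use". The section then warns that in many applications "count data have variability that far exceeds that predicted by the Poisson distribution" and expects the same here, but it names no remedy.

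The parts of the plan that determine how many days are observed are these:

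- Section 8.2 Participants: "Factoring in a potential 20% dropout of those who actually begin the protocol", 7-8 people are expected to be exposed to dronabinol.
- Section 8.9: "The primary data analysis will be an intent-to-treat analysis, which includes all randomized subjects". It adds that dropouts will be assessed as far as possible and that every analysis will be repeated in completers.
- Section 8.5.2.c: at each treatment visit subjects complete an inventory "indicating their number of days using marijuana, other drugs, and alcohol during the previous week". Section 8.5.2.b adds daily diaries, ActiWatch entries and Timeline Follow Back at the weekly visits.
- Section 8.3.1.b, Stopping Criteria: "If the subject is stopped, they will be followed for follow-up visits only". The safety monitoring text in 8.2.1.a, Dose Adjustment (8.3.1.c) and the Data and Safety Monitoring section instead keep subjects who come off medication in research visits.

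**The concern.** A log-linear model of a raw count compares the expected number of recorded days. That number is the daily rate of use multiplied by the days observed. Without an exposure term, a subject with a shorter record looks like a lighter user and also like someone with fewer abstinent days. If the arms differ in days observed, part of the treatment ratio reflects observation time, and the use and abstinence models can point in opposite clinical directions on the same data. If the arms do not differ, the varying record length is noise that the model cannot explain. Correcting for overdispersion widens the standard error but does not move a biased ratio.

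A difference between arms is plausible. The stopping criteria in 8.3.1.b concern effects of dronabinol and clonidine, so stopping could be more common in the active arm. Arms of 9 can also be unbalanced by chance.

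**Working it through.** **Inputs from the documents.** 18 subjects, "with half receiving treatment with the combination of dronabinol and clonidine and half receiving placebo" (9 per arm, 8.1); 10 weeks of treatment, or 70 days; follow-up to week 14, or 28 more days; 20% dropout overall, not split by arm or time (8.2). The documents give no alpha, power or effect size.

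**The plan's own figure.** 9 x (1 - 0.20) = 7.2, which agrees with the stated 7-8. Over both arms 18 x 0.20 = 3.6, so about 4 subjects would leave.

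**Formula.** Let dA and dP be the proportions leaving the active and placebo arms, and f the share of the window observed before leaving. With a constant daily rate and no exposure term:

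expected count ratio = true rate ratio x [1 - dA(1 - f)] / [1 - dP(1 - f)]

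With no true effect, the same factor applies to use days and to abstinent days, because both are shares of the observed days.

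| Dropouts, active v placebo | f = 0.25 | f = 0.50 | f = 0.75 |
|---|---|---|---|
| 2 v 2 | 1.00 | 1.00 | 1.00 |
| 3 v 1 | 0.82 | 0.88 | 0.94 |
| 4 v 0 | 0.67 | 0.78 | 0.89 |

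For example, 3 v 1 at mid-window gives (1 - 3/9 x 0.5) / (1 - 1/9 x 0.5) = 0.833 / 0.944 = 0.88. For dropout of 40% v 0% at mid-window the ratio is 0.80, and for 10% v 30% it is 0.95 / 0.85 = 1.12.

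**How often chance gives such splits.** If 4 of 18 leave at random, a 3:1 or worse split in either direction has probability (2 x 84 x 9 + 2 x 126) / 3060 = 58%. The 4:0 split alone has 252 / 3060 = 8%.

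**Simulation with no true effect.** Assumed, not in the documents: dropout time spread over the treatment window, dropout unrelated to use, and between-subject variation in daily use. Tests used an overdispersion-scaled standard error and a t reference on 15 df.

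| Dropout, active v placebo | Ratio, no offset | Rejection, no offset (nominal 5%) |
|---|---|---|
| 2 v 2 subjects | 0.99-1.00 | 0.2%-0.6% |
| 3 v 1 subjects | 0.88 | 2.4%-3.5% |
| 4 v 0 subjects | 0.77 | 21%-23% |
| 20% v 20%, numbers random | 1.00 | 3.4% |
| 10% v 30%, numbers random | 1.12 | 7.4% |
| 40% v 0%, numbers random | 0.81 | 15%-24% |

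The offset model gave a ratio of about 1.00 and rejection of 2.9%-6% throughout. Two variations matter. If heavier users are the ones who leave, 3 v 1 gives about 11% rejection without the offset. If the overdispersion that 8.9 expects were left uncorrected, rejection at 20% v 20% would be 24% without the offset and 3.1% with it.

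**Simulation with a true effect.** Under an assumed odds ratio of 0.25, power with the offset is over 99%. Without it, power is 87% for 2 v 2, 57% for 1 active v 3 placebo and 34% for 0 v 4. Across mean use of 60%-75% of days and between-subject SDs of 0.5-1.0 on the logit scale, with 20% dropout in each arm, the ranges are 60%-93% without and 88%-99.9% with the offset. Under a smaller assumed effect (rate ratio 0.80) and dropout of 0% active v 40% placebo, the formula gives 0.80 x 1 / 0.80 = 1.00. The effect disappears, and rejection falls from 62% to 7.5%.

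**The case against.** The point rests on silence. The sentence in 8.9 is not a full model statement, since it does not even name the treatment term, and frequency could be meant as a rate. Section 8.9 promises continued assessment of dropouts. Its completers-only replication compares subjects with roughly equal records, so it would help to expose an artefact. Diaries and Timeline Follow Back could recover missed days, and no look-back limit is stated for the latter. The trial is an 18-subject Stage 1 pilot whose outcomes are exploratory.

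Most of this stands as a limit on the size of the problem. It does not remove it: a rate is not stated, recovery of missed days is an aim and not an analysis rule, and the completers analysis conditions on an event after randomization.

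Two stronger readings are tempting. A reader might infer that the model will generally turn dropout into a treatment effect. The documents do not support that. Bias needs unequal observed days, no dropout rate by arm is given, and marked false-positive inflation with scaled errors and dropout unrelated to use appears only when all dropout is in one arm. A reader might also infer that a subject who leaves at week 3 contributes 3 x 7 = 21 of 70 treatment days. That ignores the other self-report sources and the sections that continue research visits off medication. Nor does the 20% figure say that all later days are lost.

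**Conclusion.** The concern holds in conditional form. As written, the day-count analyses have no exposure term and no rule for unobserved days.

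- **Unequal observed days:** the ratio is biased. With no effect and dropout near mid-window it is about 0.88 at 3 v 1 and 0.77-0.81 when all dropout is in the active arm, with use and abstinent days moving together. A moderate split shifts the estimate while scaled-error rejection stays near or below nominal (2.4%-3.5% at 3 v 1, 7.4% at 10% v 30%).
- **Balanced dropout:** there is no bias, but power is lost, about 87% against over 99% under the assumed odds ratio of 0.25.

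The splits, dropout times and effect sizes are assumptions. If every missed day were recovered, the problem would vanish. A chance imbalance distorts the result of the trial in hand; over repeated trials with equal dropout rates it acts as extra variance and not as bias. The point concerns outcomes that 8.9 treats as secondary. The primary GEE analysis of urine screens is not affected. The change is worth making because it is nearly free.

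**What to change.** In 8.9, add to each day-count model an offset equal to the log of the number of days with reported use data in the period (up to 70 on treatment and 28 in follow-up). Alternatively, model use days out of observed days with an overdispersed binomial, which respects the upper bound and gives one coherent test for use and abstinence. Name the overdispersion correction, say how days missed at visits are to be recovered, and report observed days by arm beside each result.

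Reconcile 8.3.1.b (follow-up visits only) with 8.2.1.a, 8.3.1.c and the Data and Safety Monitoring section (research visits continue), so that it is clear which days are meant to be observed after a subject is stopped.

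The cost is a few sentences and one variable that can be derived from self-report data already collected. The downside is that an offset assumes unobserved days resemble observed ones. If dropouts tend to relapse this fails, so a sensitivity analysis with a stated rule for missing days should accompany it. Subjects with no reported days in a period cannot enter either model and should be counted by arm.

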- 9.1. Sample Size: In order to meet the target sample of 18, We plan to screen 50 subjects ages 18-45 in the course of 20 months to achieve our desired sample size.
- 9.2. Advertising: Subjects will be recruited via websites, newspaper advertisements, flyers on campus, word-of-mouth, and the Psychotic Division Clinical Research Core. We will not specifically recruit subjects from particular patient units at McLean. Subjects may not be inpatients at McLean at the time of their participation in the study.

9.3. Inclusion criteria Inclusion:

1) Age range 18-45 years; 2) DSM-IV diagnosis of cannabis dependence, based on the Structured Clinical Interview for DSM-IV (SCID); 3) DSM-IV diagnosis of an Axis 1 psychiatric disorder, based on the Structured Clinical Interview for DSM-IV (SCID); 4) express a desire to quit cannabis use within the next 30 days; 4) have used cannabis on 20 days within the past 30 days (i.e., an average of 5 day per week); 5) identify cannabis as their primary drug of abuse; 6) stable on antipsychotic medication for 1 month; 7) for women of childbearing age, a negative pregnancy test at screening with agreement to use adequate contraception to prevent pregnancy and monthly pregnancy tests; 8) consent for us to communicate with their prescribing clinician if one exists; 9) furnish the names of 2 locators, who would assist study staff in locating them during the study period; 10) live close enough to McLean Hospital to attend study visits; 11) plan to stay in the Boston area for the next 3 months; 12) are willing and able to sign informed consent; and 13) must be psychiatrically stable, with no psychiatric medication changes in the 4 weeks prior to their screening visit.

Partners Human Subjects Research Application Form

Version Date: July 26, 2016

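### Days of use and of abstinence go to Poisson regression although the plan itself predicts much larger variance; no correction and no analysed count unit are stated

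*Combined protocol and SAP*

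**What the plan says.** The combined protocol and SAP, section 8.9 (Statistical Analysis), names the substance-use outcomes as the "number of days of cannabis use and of any substance use (and conversely, days of abstinence) during treatment and post-treatment follow-up". For the method it says "Frequency of days of cannabis use (and any substance use and days of abstinence) will be analyzed via a log-linear (or Poisson) regression model", adjusted for days of cannabis use before treatment.

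The next sentence concedes that "count data have variability that far exceeds that predicted by the Poisson distribution; we expect that days of cannabis use", with any-substance days and abstinent days included, will be no exception. The section then turns to the Addiction Severity Index (ASI) scores. Nothing there or elsewhere names a remedy for the day counts.

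The other outcomes in 8.9 do get one. Urine screens are analysed by GEE. The ASI model has "random intercepts and slopes to appropriately account for correlation among repeated measures". The mood-episode model uses GEE "to account for correlation among repeated binary outcomes on the same individual".

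The analysed unit is not given. Section 8.5.2.c describes a weekly inventory on which subjects report by "indicating their number of days using marijuana, other drugs, and alcohol during the previous week", and 8.5.2.b adds daily diaries and Timeline Follow Back. No offset or denominator for days observed is stated, although section 8.2 allows for 20% dropout.

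**The concern.** Poisson regression takes the variance to equal the mean. If the variance is larger by a factor φ, the true standard error is √φ times the one the model reports. The plan expects φ well above 1 and still leaves the model uncorrected. Fitted as written with model-based standard errors, it would give intervals that are too narrow and p-values that are too small.

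Two further problems follow.

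- Use and abstinence add up to the days observed, so they cannot both be Poisson. Separate Poisson fits can give conflicting answers from the same subject-days.
- The right correction depends on the count unit. A scale factor that works for one total per subject fails for ten weekly counts per subject.

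What is at stake is secondary inference in a pilot. The documents set no alpha and no go/no-go rule for these outcomes, so the harm is misleading intervals and p-values in the report, and a remedy chosen after the data are seen. Self-reported use is also listed among the primary measures in 8.1 and 8.9, so the day counts are not peripheral.

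**Working it through.** The plan gives no power, alpha or dispersion figure for this analysis, so there is no figure of its own to reproduce.

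**Inputs from the documents**
- 18 subjects, half to each arm, so 9 per arm (8.1). Section 8.2 also says "14-18 will probably end up being randomized", so 7 per arm was checked too.
- A 10-week treatment period, 70 days (8.1).
- The entry criterion "have used cannabis on 20 days within the past 30 days" (9.3), which is 20/30 = 67%.

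**Assumptions**
- Two-sided 5% tests and model-based standard errors.
- On-trial mean use p of 67% as an anchor, with 40–60% as alternatives.
- Within-person correlation (ICC) of 0.05 to 0.3.
- A 28-day follow-up window for weeks 11–14. The plan does not define one.

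**Step 1: error rate for a given φ.** Error = 2 × [1 − Φ(1.96/√φ)].

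| φ | True SE / reported SE | Error at nominal 5% |
|---|---|---|
| 1.5 | 1.22 | 11% |
| 2 | 1.41 | 17% |
| 4 | 2.00 | 33% |

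**Step 2: φ for a count of m days.** With person-specific use probabilities, φ(use) = (1 − p)(1 + (m − 1)ICC) and φ(abstinence) = p(1 + (m − 1)ICC).

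For p = 2/3, m = 70 and ICC = 0.1:
- Use: (1/3)(1 + 6.9) = 2.63, which gives an error of 23%.
- Abstinence: (2/3)(1 + 6.9) = 5.27, which gives an error of 39%.

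Setting φ = 1 gives the ICC above which Poisson errors are too small. At p = 2/3 and 70 days it is 2/69 = 0.029 for use and 0.5/69 = 0.007 for abstinence. At 28 days it is 2/27 = 0.074 and 0.5/27 = 0.019.

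**Step 3: null simulation.** Beta-binomial days, no treatment effect, arm plus log baseline days in the model, 6,000 runs per setting. Baseline was 20–30 of 30 days, with assumed correlation 0 or 0.5 to on-trial use. Ranges run over ICC 0.05–0.3.

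| Setting | Poisson, use | Poisson, abstinence | Quasi-binomial t |
|---|---|---|---|
| 70 days, 67% use, 9 per arm | 8–47% | 21–62% | 4–5% |
| 70 days, 40–60% use, 9 per arm | 9–60% | 11–59% | 4–5% |
| 28 days, 67% use, 9 per arm | 2–26% | 9–43% | 4–5% |
| 70 days, 67% use, 7 per arm | 8–47% | 21–61% | 4–5% |

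For 70-day totals, the quasi-Poisson t test for use held 3–5%. At 67% use over 70 days, use and abstinence disagreed on significance in 13–18% of null datasets. With ICC = 0, plain Poisson was conservative: 0.1% for use and 1.7% for abstinence.

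**Step 4: does the unit matter?** With complete weeks and subject-level covariates, plain Poisson gives the same answer either way. In one dataset, totals and ten weekly counts both gave an estimate of −0.2184 with SE 0.0687. The remedy does depend on the unit. For ten weekly counts at 67% use:
- scale factor alone: 26–51% error;
- subject-clustered sandwich z test: 8–10%;
- small-sample-corrected clustered t test (15 df): 4–5%.

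The scale factor fails because it sees only the spread of single weekly counts. At ICC 0.2 it averages 0.62–0.69 for weekly use, against 4.2–5.2 for the 70-day total.

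**The case against.** The strongest reply is that the plan never says model-based standard errors will be used. The overdispersion sentence reads as the lead-in to a correction that may have been lost in editing. That is plausible, and it is why the consequence is stated conditionally. The text still names no correction, and several non-equivalent ones are available.

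The second reply concerns the 67% anchor. It is an entry level, and baseline use spread evenly over 20–30 days would average 25/30 = 83%. At 83% over 70 days, simulated Poisson error for days of use was 1.9% at ICC 0.05, 7.5% at 0.1 and 29% at 0.3. Over 28 days it was 0.4–10.3%. The ICC threshold for use rises to 5/69 = 0.072 (70 days) or 5/27 = 0.185 (28 days). This stands: for days of use, plain Poisson can be conservative. Abstinence at 83% remained inflated at 15–64%.

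Three smaller points also stand.
- Period totals are a natural reading of 8.9, and the diaries could supply them, but the plan does not say so.
- The equality of weekly and total fits needs complete follow-up or an offset. In one dataset with four early dropouts, totals without an offset gave −0.2011 and weekly counts −0.2081.
- Any-substance days are adjusted only for pre-treatment cannabis days.

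The exploratory status of these outcomes limits the severity. It does not make the standard errors right.

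**Conclusion.** The concern holds. The plan assigns a model, predicts that its variance assumption will fail for all three day counts, and states neither a correction nor the analysed unit. Confidence in the omission is high.

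The size depends on dispersion, which the documents do not give. If the predicted excess variance is present and standard errors are model-based, the nominal 5% error plausibly runs from about 10% to well above 30%, usually worse for abstinence than for use when use is above 50%. If within-person correlation is low or use stays near its ceiling, the error for days of use can fall below 5%. Plain Poisson is therefore unreliable in either direction, and a dispersion-scaled test corrects both. This should be fixed before analysis; it affects secondary inference in a pilot of 18.

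**What to change.** In 8.9:

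1. State that the outcome is one total per subject per period (treatment, follow-up), and define the days in each period.
2. Replace plain Poisson with a dispersion-scaled model and a t reference. Quasi-binomial regression of days used out of days observed is preferable, because it gives the same test for use and for abstinence. Quasi-Poisson with log days observed as offset is an acceptable alternative.
3. Keep the baseline cannabis-days covariate. Use the same model for any-substance days, and say whether pre-treatment any-substance days should be the covariate there.
4. If weekly counts are preferred, specify a variance clustered by subject with a small-sample correction and a t reference, since a scale factor alone is not enough.

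The cost is two or three sentences and a standard software option, with no new data. Intervals will usually be wider.

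### The ASI mixed model in section 8.9 names no baseline adjustment; a common baseline mean would gain precision at almost no cost

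*Combined protocol and SAP*

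**What the plan says.** Section 8.9 analyses changes in the ASI Drug and Alcohol composites with a linear mixed model in PROC MIXED, with random intercepts and slopes. The treatment effect is read "as determined by the group-by-time interaction in the linear mixed effects regression models". The fixed effects are not listed. Nothing says whether baseline ASI is an outcome or a covariate, or whether the arms share a baseline mean.

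The other secondary models in 8.9 are explicit. The day-count model is fitted "controlling for pre-treatment frequency of days of cannabis use", and for mood episodes "the logistic regression model will include the effects of treatment condition and the baseline measure of the outcome".

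Under 8.5.2.c, cannabis and other substance use severity "will be assessed at baseline and weeks 5,10, and 14 with the Addiction Severity Index", and the composites are called secondary measures. Table 1 places the baseline ASI at the baseline-2 visit, before treatment starts. Randomisation (8.2.1.c) is stratified on daily versus non-daily use, not on ASI.

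**The concern.** In the usual group, time and group-by-time model, baseline ASI is one of the outcomes and each arm has its own baseline mean. The test is then a difference in change. Baseline-2 precedes treatment, so randomisation makes the two baseline means equal in expectation. Estimating them separately spends information that a very small trial could use.

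There is also a conditional effect. If one arm happens to start higher, part of that excess is transient and tends to recede, so that arm appears to improve more. With about 9 subjects per arm, chance differences at baseline are not small. At stake are the precision of a secondary result and how it reads once a baseline imbalance has been seen.

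**Working it through.** **Inputs from the documents.** Section 8.2: "A total of 18 cannabis-dependent volunteers with (9 men, 9 women) an Axis 1 psychiatric Disorder will serve as subjects". Section 8.1: "with half receiving treatment with the combination of dronabinol and clonidine and half receiving placebo", so 9 per arm. ASI times are weeks 0, 5, 10 and 14 (8.5.2.c). Section 8.2 also allows for attrition ("Factoring in a potential 20% dropout of those who actually begin the protocol"), and 9 x 0.8 = 7.2, which agrees with its 7-8 people exposed. The documents give no ASI SD, correlation, effect size or power, so there is no planned figure to reproduce.

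**Assumptions.** Baseline SD = 1; ICC 0.3-0.9; random-slope SD (s) 0-0.5 baseline SD per 10 weeks; intercept and slope uncorrelated; complete data; linear time; variance components known.

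**Chance imbalance.** SE of the baseline difference = sqrt(2/9) = 0.47 SD, or sqrt(2/7) = 0.53 SD with 7 per arm. P(|difference| >= 0.5 SD) = 29% with 9 per arm.

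**Variance of the slope difference.** In units of 10 weeks the times are 0, 0.5, 1.0 and 1.4, with mean 0.725 and sum of squares about the mean 1.1075. Apart from the common factor 2/9, the estimated intercept and slope differences have:
- V22 (slope) = s² + (1 - ICC)/1.1075
- V12 = -(1 - ICC) x 0.725/1.1075 = -0.6546 x (1 - ICC)
- V11 (intercept) = ICC + (1 - ICC) x (1/4 + 0.725²/1.1075) = ICC + 0.7246 x (1 - ICC)

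With free baseline means the slope variance is V22. With a common baseline mean it is V22 - V12²/V11.

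At ICC 0.5 and s = 0.3: V22 = 0.09 + 0.4515 = 0.5415; V12 = -0.3273; V11 = 0.8623. Common-baseline variance = 0.5415 - 0.1242 = 0.4173. Ratio = 0.771, comparable to 18/0.771 = about 23 subjects instead of 18.

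Ratio of common-baseline to free-baseline variance:

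| ICC | s = 0 | s = 0.3 | s = 0.5 |
|---|---|---|---|
| 0.3 | 0.588 | 0.640 | 0.705 |
| 0.5 | 0.725 | 0.771 | 0.823 |
| 0.7 | 0.845 | 0.884 | 0.919 |
| 0.8 | 0.900 | 0.933 | 0.958 |
| 0.9 | 0.951 | 0.976 | 0.987 |

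The intercept-slope correlation matters too. At ICC 0.5 and s = 0.4 the variance saving is 32%, 20% and 11% for correlations of -0.3, 0 and 0.3.

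**Shift given an imbalance.** Per 1 SD of baseline difference, the free-baseline contrast over 10 weeks moves by -0.6546 x (1 - ICC). For a one-SE imbalance:
- ICC 0.5: 0.327 x 0.47 = about 0.15 SD
- ICC 0.8: 0.131 x 0.47 = about 0.06 SD

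**Simulation (40,000 trials per scenario, 9 per arm).** With no treatment effect, the free-baseline estimate averaged between -0.002 and 0.002, with type I error 4.8-5.1%. Among trials with an imbalance above 0.47 SD in either direction, null rejection was 9% at ICC 0.3, 7-8% at 0.5 and about 6% at 0.8. Power for a 0.8 SD effect per 10 weeks, free baseline against baseline covariate:

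| ICC | s = 0.2 | s = 0.4 |
|---|---|---|
| 0.5 | 62% vs 70% | 53% vs 58% |
| 0.8 | 92% vs 92% | 78% vs 77% |

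**The case against.** **The plan does not say the arms differ at baseline.** A reader might infer that 8.9 commits to separate baseline means. It does not: a common-baseline model would also be tested by the group-by-time interaction. This stands, and the plan cannot be called wrong on that ground. The free-baseline form is only the default reading. If instead only weeks 5, 10 and 14 are outcomes, with no baseline term, the interaction measures divergence after week 5 and misses an effect already present by then. Stating the handling of baseline helps under every reading.

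**The analysis is not invalid.** A reader might infer bias or an inflated type I error. Neither follows: the shift is conditional on the imbalance observed and averages out over randomisations. Nor should the shift be taken from a two-point change score, where (1 - 0.5) x 0.47 = 0.24 SD at correlation 0.5. The planned model fits a slope to four visits, for which the figure is 0.15 SD.

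**The gain may be small.** This stands for high correlations. A two-time-point baseline covariate, with a small-sample factor of (18 - 3)/(18 - 4), cuts variance by 20% at correlation 0.5 and 4% at 0.8, and costs about 2% at 0.9. So adjustment does not gain at every correlation below 1 in a trial of 18.

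**The schedule may include Week 1.** Table 1 appears to mark the ASI there, although its columns are hard to read in the available copy and 8.5.2.c does not list it. Adding Week 1 moves the ratio at ICC 0.5, s = 0.3 from 0.77 to 0.86, the range for ICC 0.3-0.7 to 0.71-0.96, and the one-SE shift at ICC 0.5 to about 0.10 SD.

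**Little depends on this test.** The trial is a Stage 1 pilot and ASI is secondary. This limits the priority but does not remove the gain.

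**Conclusion.** The point holds as a near-free improvement to an under-specified model. Baseline ASI is already collected, two sister models in 8.9 use their baselines, and the ASI model names none.

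Under the stated assumptions, a common baseline mean would leave 59-92% of the default model's slope variance at ICC 0.3-0.7 (standard error 4-23% smaller) and about 90-99% at ICC 0.8-0.9. The true ASI correlation is not in the documents, so the size within that range is unknown. These ratios treat the variances as known, so the realised gain in 14-18 subjects (8.2: "14-18 will probably end up being randomized") may be somewhat smaller. Priority is low to moderate.

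**What to change.** In 8.9, state that the ASI model assumes a common baseline mean. In PROC MIXED, code time as zero at baseline-2, omit the group main effect, and let group enter only through post-baseline terms. The group-by-time test then stays as planned.

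Alternatively, model weeks 5, 10 and 14 with the baseline-2 composite as covariate. This is not the same analysis: the test must become the group effect, overall or at a named visit, because the interaction alone would capture only divergence after week 5.

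Either version takes one sentence and a small change of code, with no new data. The covariate version spends one degree of freedom and drops any subject without a baseline ASI; the common-baseline version keeps such a subject. State in the same place whether the ASI is taken at Week 1, so that the list of visits in the model is fixed.
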